## **Brief Summary**

The purpose of this study is to quantify the therapeutic efficacy and role of trained service dogs on socio-emotional functioning among military veterans with posttraumatic stress disorder (PTSD).

## **Detailed Description**

The long-term research goal is to evaluate the safety and efficacy of service dogs as a complementary intervention to enhance biopsychosocial functioning in special populations. The objective is to conduct a methodologically rigorous trial to quantify the therapeutic efficacy of service dogs on clinically important outcomes for veterans with PTSD. Based on preliminary findings and qualitative reports, the central hypothesis is that military veterans with PTSD who are provided service dogs will experience reduced PTSD symptoms related to socio-emotional functioning and arousal modulation. The rationale for this research is that its successful completion will provide an evidence-based demonstration of the efficacy and role of an increasingly used yet poorly tested complementary intervention. The completion of this project is expected to establish an initial demonstration of the therapeutic efficacy of service dogs in this population, as well as possible mechanisms of action via specific biological pathways and human-canine interaction profiles.

Conditions: Posttraumatic Stress Disorder (PTSD)

Intervention / Treatment: Behavioral: Service Dog

## **Funding**

This work was supported by the Eunice Kennedy Shriver National Institute of Child Health and Human Development (NICHD) and the National Center for Complementary and Integrative Health (NCCIH) of the National Institutes of Health (NIH) under award number R21HD091896, Merrick PetCare and the Dogtopia Foundation. The content is solely the responsibility of the authors and does not necessarily represent the official views of the National Institutes of Health.

## **Participant Criteria**

### Eligibility Criteria

Inclusion criteria for veterans into the study will include:

- Applied for and approved to receive a dog from K9s For Warriors
- Military service on or after September 11, 2001
- Honorable discharge or current honorable service
- Diagnosis of PTSD
- No conviction of any crimes against animals.
- 18 Years and older

## **Study Plan**

### Study Design

*Primary Purpose:* Supportive Care

*Allocation:* Non-Randomized

*Interventional Model:* Parallel Assignment

*Masking:* Single (Outcomes Assessor)

*Masking Description:* Clinician Administered PTSD Scale for DSM-V (CAPS-5) assessments will be completed via telephone by a trained CAPS-5 rater who will be masked to the intervention and treatment arm of each participant.

### Arms and Interventions

Participant / Group Arm	Intervention / Treatment
Experimental: Service Dog Participants in the service dog arm will receive unrestricted, non-study usual care, in addition to a trained service dog.	Behavioral: Service Dog A service dog trained to perform tasks that are specific to PTSD
No Intervention: Waitlist Control Participants in the control arm will receive unrestricted, non-study usual care, while on the waitlist for a service dog.	

## **Outcome Measures**

Primary

Outcome Measure	Measure Description	Time Frame
PTSD severity and symptoms via self-report	Posttraumatic Stress Disorder Checklist for DSM-V (PCL-5)	3 months
PTSD severity and symptoms via clinician rating	Clinician-Administered PTSD Assessment for the Diagnostic and Statistical Manual of Mental Disorders, Fifth Edition DSM-V (CAPS-5)	3 months
Depression	Patient Reported Outcome Measurement Information System (PROMIS) Adult Short Form (SF) v1.0 - Emotional Distress - Depression 8a	3 months
Anxiety	Patient Reported Outcome Measurement Information System (PROMIS) Adult Short Form (SF) v1.0 - Emotional Distress - Anxiety 8a	3 months

Secondary

Outcome Measure	Measure Description	Time Frame
Social isolation	Patient Reported Outcome Measurement Information System (PROMIS) Adult Short Form (SF) v2.0 - Social Isolation 8a	3 months
Companionship	Patient Reported Outcome Measurement Information System (PROMIS) Adult Short Form (SF) v2.0 - Companionship 6a	3 months
Ability to participate in social activities	Patient Reported Outcome Measurement Information System (PROMIS) Adult Short Form (SF) v2.0 - Ability to Participate in Social Roles and Activities 8a	3 months
Mental health quality of life	Veterans Rand 12-item Health Survey (VR-12) - Mental Health Component	3 months
Psychological well-being	Bradburn Scale of Psychological Wellbeing (BSPW)	3 months
Life satisfaction	Satisfaction with Life Scale (SLS)	3 months
Resilience	Connor-Davidson Resilience Scale (CDRS)	3 months
Anger	Patient Reported Outcome Measurement Information System (PROMIS) Adult Short Form (SF) v1.1 - Emotional Distress - Anger 5a	3 months
Daily socio-emotional experiences	Ecological momentary assessment (EMA)	3 months

Other Pre-specified

Outcome Measure	Measure Description	Time Frame
Work and activity participation	Work Productivity and Activity Impairment Questionnaire (WPAIQ)	3 months
Suicidal ideation	Columbia Suicide Severity Rating Scale (CSSRS)	3 months
Sleep quality	Pittsburgh Sleep Quality Assessment (PSQI)	3 months
Sleep disturbance	Patient Reported Outcome Measurement Information System (PROMIS) Adult Short Form (SF) v1.0 - Sleep Disturbance 8a	3 months
Sleep actigraphy	Actiwatch 2 (Philips Respironics)	3 months
Salivary cortisol awakening response	Passive drool method (Salimetrics)	3 months
Electrodermal activity (skin conductance)	Embrace wristband (Empatica, Inc.)	3 months

### Collaborators

- Eunice Kennedy Shriver National Institute of Child Health and Human Development (NICHD)
- National Center for Complementary and Integrative Health (NCCIH)

## **Statistical Analysis Plan**

Since all the outcome measures are ordinal in nature (based on questionnaire scores), cumulative probability models will be used for all outcomes. While many of these outcomes have been modeled with linear regression in past studies, statisticians have cautioned that treating ordinal data as though they were continuous could potentially lead to misleading results, and that even continuous data can be modeled with cumulative probability models to avoid assumptions about the conditional distribution of the outcome (1,2). Cumulative probability models enable estimation of effect ratios (e.g., veterans allocated service dogs had a lower odds of greater CAPS-5 score compared to veterans on the waiting list), exceedance probabilities (e.g.  $\text{Prob}[\text{PHQ-9} \geq 10 | \text{X}=\text{service dog}]$ ), and differences in exceedance probabilities (e.g. absolute risk reduction between veterans allocated a service dog vs control).

In addition to a binary variable for intervention (1=service dog, 0=control), covariates will include the baseline value of the modeled outcome, age, gender/sex, concurrent evidence-based treatment for PTSD, pet ownership, military sexual trauma, and traumatic brain injury.

We will conduct sensitivity analyses, modeling the primary outcomes with ordinary least squares regression to see if our conclusions are sensitive to the model choice, by comparing the estimated conditional means and 95% confidence intervals.

In exploratory analyses, we will consider a potential interaction between treatment and baseline PTSD severity, as baseline severity could modify the effect of service dog.

Multiple imputation will be used for missing covariate data and missing data at the 3-month follow-up visit.

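### Arms are not randomised, yet the depression, anxiety and psychosocial models do not adjust for baseline PTSD severity

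*Combined protocol and SAP*

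**What the plan says.** - **Allocation.** Study Design lists it as "Non-Randomized". Every participant has "Applied for and approved to receive a dog from K9s For Warriors" (Eligibility Criteria). Controls have usual care "while on the waitlist for a service dog" (Arms and Interventions). The documents do not say what decides who gets a dog and who waits.
- **Outcomes.** The four primaries are PCL-5, CAPS-5, PROMIS "Emotional Distress - Depression 8a" and PROMIS "Emotional Distress - Anxiety 8a". Eight secondaries are questionnaires: isolation, companionship, social participation, VR-12 mental health, well-being, life satisfaction, resilience and anger.
- **Covariates.** The Statistical Analysis Plan has one list for all outcomes: "covariates will include the baseline value of the modeled outcome, age, gender/sex", then current evidence-based PTSD therapy, owning a pet, sexual trauma in service, and brain injury.
- **Severity elsewhere.** It appears once more, as an exploratory analysis: "we will consider a potential interaction between treatment and baseline PTSD severity". The reason given is "as baseline severity could modify the effect of service dog". No outcomes are named.
- **Sensitivity analysis.** Ordinary least squares replaces the ordinal model for the primaries. No change of covariates is stated.

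**The concern.** Without randomisation, the adjusted comparison is only as good as the covariate list. The documents describe no matching, weighting or propensity method. PTSD is the condition under study, so its baseline severity is an obvious candidate confounder, yet two of the four primaries and eight secondaries are modelled without it.

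Bias from this source needs two conditions together: the arms differ in baseline severity, and severity predicts the 3-month outcome after conditioning on that outcome's own baseline. If both hold, part of the reported difference in depression, anxiety or psychosocial functioning existed before any dog was placed. It could flatter the dog arm or count against it.

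Neither planned extra analysis closes the gap. The least-squares analysis tests the model form. The interaction model would normally carry a severity main effect, but it is exploratory and tied to no outcome.

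**Working it through.** The plan has no figure to reproduce: it gives no sample size, baseline data or correlations. The check is a reading of the covariate list, followed by a bias calculation on assumed inputs.

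**1. Where severity enters the main models**

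| Outcome | Own baseline is a PTSD score? | Severity adjusted? |
|---|---|---|
| PCL-5, CAPS-5 | yes | yes |
| Depression, anxiety (primary) | no | no |
| Eight questionnaire secondaries | no | no |

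That leaves 2 + 8 = 10 models without it.

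**2. Assumed inputs**

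- d: arm difference in severity, 0.2-0.3 SD, with 0.5 SD as the extreme.
- ρ: correlation of severity with baseline depression, 0.6 (range 0.5-0.7).
- g: effect of severity on the outcome given its own baseline, 0.15-0.25.
- Own-baseline coefficient 0.45, logistic residual SD 0.75, no true treatment effect.
- Baseline depression differs between arms only through severity.

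**3. By hand, adjusting for own baseline only**

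Bias = g × d × (1 − ρ²). With g = 0.25, d = 0.3, ρ = 0.6:

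- Bias = 0.25 × 0.3 × 0.64 = 0.048.
- Outcome variance = 0.45² + 0.25² + 2 × 0.45 × 0.25 × 0.6 + 0.75² = 0.9625, so SD = 0.981 and the bias is 0.048 / 0.981 = 0.049 SD.
- Logistic scale = 0.75 × √3/π = 0.4135, so the odds ratio is exp(0.048 / 0.4135) = 1.12.
- Unadjusted bias = 0.3 × (0.45 × 0.6 + 0.25) = 0.156, so own baseline absorbs 1 − 0.048/0.156 = 69%. With g = 0.15 it absorbs 1 − 0.096/0.42 = 77%.

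A linear simulation of 2,000,000 records at d = 0.3, ρ = 0.6, g = 0.2 gave 0.038 SD without severity (formula 0.0384) and −0.0004 with severity measured without error.

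**4. Proportional-odds simulation with the whole SAP list**

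The outcome was cut into 20 levels. PTSD therapy, sexual trauma and brain injury each had latent correlation 0.25 with severity. Each scenario used 15 samples of 200,000 (Monte Carlo SE of the log odds ratio about 0.002). Here r is the reliability of the added severity score.

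| d | g | OR, SAP list | + severity, r = 0.9 | r = 0.8 | r = 0.7 |
|---|---|---|---|---|---|
| 0 | 0.25 | 1.000 | 0.999-1.000 | 0.999-1.000 | 0.999-1.000 |
| 0.2 | 0.15 | 1.044 | 1.007 | 1.013 | 1.018 |
| 0.2 | 0.25 | 1.072 | 1.011 | 1.021 | 1.029 |
| 0.3 | 0.15 | 1.066 | 1.010 | 1.019 | 1.027 |
| 0.3 | 0.25 | 1.110 | 1.017 | 1.032 | 1.045 |
| 0.5 | 0.25 | 1.189 | 1.028 | 1.054 | 1.076 |
| −0.5 | 0.25 | 0.840 | 0.972 | 0.948 | 0.928 |

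The full list absorbs about 71-78% of the unadjusted bias at ρ = 0.6. With ρ = 0.5 or 0.7, the 0.3/0.25 row becomes 1.129 or 1.090, and the 0.5/0.25 row 1.223 or 1.154.

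**5. What the added score leaves behind**

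Approximate share of bias remaining = e / (e + 1 − ρ²), with e = (1 − r)/r. At r = 0.8: 0.25 / (0.25 + 0.64) = 28%. The simulation gave about 16%, 30% and 43% for r = 0.9, 0.8 and 0.7.

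**6. Type I error**

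Assumed N = 150 and r = 0.8; 3,000 trials, bootstrap percentile 95% interval with 250 resamples; Monte Carlo SE 0.4-0.5 points.

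| d | g | SAP list | + severity |
|---|---|---|---|
| 0 | 0.25 | 5.4% | 5.0% |
| 0.2 | 0.15 | 5.2% | 5.2% |
| 0.3 | 0.15 | 5.7% | 5.1% |
| 0.3 | 0.25 | 6.3% | 5.2% |
| 0.5 | 0.25 | 8.4% | 4.9% |

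Neither multiple imputation nor the Bayesian fit that the Software section allows was simulated.

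**The case against.** The strongest reply is about weight.

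- **No evidence of imbalance.** Both arms are approved applicants to one provider and all have a PTSD diagnosis; nothing suggests that placement depends on severity. This stands. So does the remark that the undescribed allocation mechanism is the larger gap. But while that mechanism is unknown, balance cannot be assumed either.
- **The range presupposes a problem.** A coefficient below 0.15 is possible. At g = 0.05 and d = 0.3 the bias is 0.05 × 0.3 × 0.64 = 0.0096, about 0.011 SD or an odds ratio of 1.02; at zero there is none. This stands, and the figures should be read as conditional.
- **Effect modification is not confounding.** The SAP's reason for the interaction does not show that severity predicts depression or anxiety. If severity matters only in the dog arm, it predicts the outcome there, but omitting it mainly changes whose average effect is estimated. The SAP may also have had only the PTSD scales in mind. This largely stands: the rationale shows that the authors think severity relevant, not that it confounds these outcomes.
- **Small effect, partial remedy.** Existing covariates absorb most of the bias, and an imperfect score leaves some of the rest. This is true, but it bears on size only.
- **A sensitivity analysis would do.** That is a workable lesser option. It would leave the main estimates for two primaries without the covariate, for a saving of one parameter each.

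**Conclusion.** The concern holds as a should-fix point of modest size. The omission is plain from the text. Its consequence is conditional on an arm difference in severity and on severity predicting the outcome beyond its own baseline; the documents give no data on either.

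Under the assumed inputs, differences of 0.2-0.3 SD leave about 0.02-0.05 SD, or an odds ratio of 1.04-1.11 (up to 1.13 at correlation 0.5). Only the extreme corner, 0.5 SD with coefficient 0.25, reaches 1.19, or 0.84 if the dog arm is the less severe. The issue is bias in the estimate; false-positive risk is little affected outside that corner. Confidence is medium, because every numerical input is an assumption.

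**What to change.** Before outcome data are analysed, add one sentence to the SAP: baseline PTSD severity, as one named score (CAPS-5 or PCL-5 total, one degree of freedom), is a covariate in the depression and anxiety primary models and in the eight questionnaire secondary models. Report baseline severity by arm, and state that the adjustment reduces confounding by severity without fully removing it. Extending it to the EMA and the other pre-specified outcomes is optional.

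No new data are needed: both scores are already required as baselines for their own models, and the planned multiple imputation of covariates would cover missing values. The timing matters because the Reporting section ties every estimate to covariates fixed in advance.

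The cost is one term in ten models. With an assumed 20-level outcome and N = 150, the model standard error rises by 0.5-1.6% and the bootstrap SD by 1.7-2.7%. This was not examined for sparse or physiological outcomes.

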## **Reporting**

1. Estimated conditional median (or mean) (e.g., conditional mean PCL-5 given service dog, and given no service dog), with nonparametric bootstrap 95% confidence intervals; adjusted for pre-specified covariates.
2. Estimated parameter comparing service dog group to no service dog group (e.g. odds ratio for logit link) with nonparametric bootstrap 95% confidence interval; adjusted for pre-specified covariates.
3. For established clinically important cutoffs, exceedance probabilities ( $\text{Prob}[Y \geq y | X]$ ) will be reported (e.g.,  $\text{Prob}[\text{PHQ-9} \geq 10 | \text{X}=\text{service dog}]$ ), and differences in exceedance probabilities with nonparametric bootstrap 95% confidence intervals; adjusted for pre-specified covariates.

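### Does leaving the timing of the PTSD-treatment covariate unstated put the adjusted service-dog estimates at risk?

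*Combined protocol and SAP*

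**What the plan says.** The covariate list in the Statistical Analysis Plan section reads "covariates will include the baseline value of the modeled outcome, age, gender/sex, concurrent evidence-based treatment for PTSD", and goes on to traumatic brain injury, military sexual trauma and whether the veteran owns a pet. Only one entry carries a date: "the baseline value of the modeled outcome". The list serves the models for every outcome, including the four primary ones (PCL-5, CAPS-5, PROMIS depression and PROMIS anxiety, all at 3 months). Under Reporting, each of the three kinds of estimate is "adjusted for pre-specified covariates".

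Three other statements bear on the point:

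- Study Design gives the allocation as "Non-Randomized".
- Arms and Interventions says of one arm "Participants in the service dog arm will receive unrestricted, non-study usual care, in addition to a trained service dog", and of the other "Participants in the control arm will receive unrestricted, non-study usual care, while on the waitlist for a service dog".
- On missing data: "Multiple imputation will be used for missing covariate data and missing data at the 3-month follow-up visit".

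**The concern.** A treatment described as concurrent must be concurrent with something, and the intervention period is one candidate. Since neither arm is restricted in the care it receives, veterans may start or stop therapy after placement. A covariate recorded then would be a post-placement variable.

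The arms define a total contrast: dog added to usual care against usual care alone. If having a dog makes veterans more or less likely to take up therapy, that change belongs to the total effect. Holding follow-up therapy fixed would remove it, and the coefficient would answer a different question. The shift could go either way and would run through all four primary outcomes and every reported quantity. If therapy and outcome also share an unmeasured cause, the coefficient need not equal the direct effect either.

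**Working it through.** **1. What the text fixes.** No section dates the treatment covariate. The missing-data sentence names covariates and the 3-month visit separately, but that is at most a faint hint and does not settle the timing. The company the covariate keeps says more: a baseline score, age, gender/sex, injury and trauma history, and pet ownership. None is described as a follow-up measurement.

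**2. Two readings.** (a) Therapy status before placement: adjustment is proper, because allocation is not randomized and existing therapy may differ between arms. (b) Therapy during follow-up: the concern applies, provided that the dog changes uptake.

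**3. Size under reading (b).** The documents give no effect sizes, so every input here is assumed. Let the direct effect be -0.30 SD, *e* the effect of therapy on the outcome, and *d* the change in therapy uptake caused by the dog, with no shared unmeasured cause.

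Total effect = -0.30 + *e* × *d*. Estimate adjusted for follow-up therapy = -0.30.

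| *e* | *d* | Total | Adjusted | Adjusted relative to total |
|---|---|---|---|---|
| -0.3 | +0.10 | -0.330 | -0.30 | 9.1% smaller |
| -0.5 | +0.20 | -0.400 | -0.30 | 25.0% smaller |
| -0.3 | -0.10 | -0.270 | -0.30 | 11.1% larger |
| -0.5 | -0.15 | -0.225 | -0.30 | 33.3% larger |
| either | 0 | -0.300 | -0.30 | no difference |

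At 10 points the gap is 0.3 × 0.10 = 0.03 SD to 0.5 × 0.10 = 0.05 SD.

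Because the planned models are ordinal, the same effects were also tried in a proportional-odds simulation (five-level outcome, 35% uptake in controls). The log odds ratio was about 9-22% smaller for +10 to +20 points and 13-38% larger for -10 to -15 points. At zero shift it was 1-4% larger, from non-collapsibility alone.

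**4. What reading (a) delivers.** In a simulation of 1,000,000 subjects (baseline therapy 30% in the dog arm and 40% in controls, *e* = -0.5, *d* = +0.20, true total -0.400), the unadjusted estimate was -0.372, the baseline-adjusted one -0.400 and the follow-up-adjusted one -0.300. Baseline adjustment recovers the total effect here, but the set-up assumes that every later difference in uptake beyond the baseline imbalance is caused by the dog.

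**5. Relaxing that assumption.** Without randomization, later therapy may also differ between arms for reasons unrelated to the dog and not captured by baseline status. Call that difference *d0*, and let the dog have no effect on uptake, so the true effect is -0.30.

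Baseline-adjusted estimate = -0.30 + *e* × *d0*.

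- *e* = -0.3, *d0* = ±0.10: -0.33 or -0.27, an error of 0.03 SD.
- *e* = -0.5, *d0* = ±0.10: -0.35 or -0.25, an error of 0.05 SD.

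Simulation gave the same values, with the follow-up-adjusted estimate close to -0.30 each time.

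**6. Comparison.** For a 10-point difference, the error from adjusting too late (step 3) and the error from adjusting only at baseline (step 5) are equal: 0.03 to 0.05 SD. Which applies depends on why therapy differs, and the documents do not say.

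**The case for a change.** The best case for amending the plan is that two analysts could follow it faithfully, build different variables, and both call the result pre-specified. The planned sensitivity analysis would not expose this, because it swaps the ordinal model for least squares and leaves the covariates alone. A few words dating the covariate would cost almost nothing, and would be harmless if baseline was meant all along.

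Part of this stands. The timing is unstated, the least-squares comparison is silent on it, and for the total contrast the usual choice is a pre-placement value. The rest is weaker. If baseline was meant, the added words alter no estimate. If follow-up was meant, unrestricted care shows that therapy *may* change, not that the dog changes it, and with no such effect the two adjustments agree in a linear model. Nor is fixing the covariate at baseline, with later therapy left to description, clearly the safer course here: a by-arm table would reveal an arm difference unrelated to the dog, but would not correct for it. The documents also do not say how treatment status is collected, so a baseline value is itself an assumption.

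**Conclusion.** No change is needed. The plan leaves out a detail that analysts would ordinarily fill with status before placement, in line with the rest of the list; carried out that way, the analysis is sound on this point. The alternative reading does harm only if the dog also alters therapy use within 3 months. Even then, the shift under the assumed effects is 0.03 to 0.05 SD per 10 points of uptake, which baseline-only adjustment can match in error when the arms differ in later therapy for other reasons. The percentages (9-25% smaller, 11-33% larger) are hypothetical: direct effect, therapy effect and uptake shift are all assumed, and a shared unmeasured cause is left out. The conclusion would be different if the documents stated that the covariate is a 3-month value, or gave grounds to expect the dog to change therapy use. They do neither.
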